6.13. Efficacy Analyses

The analyses described in Section 6.13 will include data collected prior to permanent discontinuation (i.e., last dose) of IP in each 6-week treatment period, for all randomized patients.

The longitudinal observations of actual and change from baseline in HbA1c during the 12-week treatment period will be summarized by period and by treatment sequence. HbA1c reflects patients' blood glucose control over the past 2-3 months and therefore there may be potential carryover effect from Period I to Period II. For this reason, no treatment comparison will be conducted.

Actual and change from baseline 1,5-AG values will be compared between LY900014 and insulin lispro using MMRM defined in Section 6.1.

6.14. Subgroup Analyses for Primary Endpoint

The following subgroups will be explored to evaluate consistency of treatment effects on the primary safety measure using data collected from the Safety Population excluding data that are collected while patients temporarily are off pump or off IP:

- Duration of CSII use (using the median as the cutoff)
- Region (US, OUS)
- Pump Model

In addition, the primary endpoint will be assessed in the subset of patients with HbA1c \leq 8% level at entry.

Exploratory subgroup analyses or summaries of hypoglycemic event data on historical use of SmartGuard/Threshold Suspend (Yes, No) will also be conducted on the Safety Population.

Additional exploratory subgroup analyses may also be performed.

6.15. Interim Analyses and Data Monitoring

No interim analyses are planned for this study. If an unplanned interim analysis is deemed necessary, the appropriate Lilly medical director, or designee, will be consulted to determine whether it is necessary to amend the protocol.

6.16. Clinical Trial Registry Analyses

Additional analyses will be performed for the purpose of fulfilling the Clinical Trial Registry (CTR) requirements.

Analyses provided for the CTR requirements include the following:

Summary of AEs, provided as a dataset which will be converted to an XML file. Both SAEs and 'Other' Non-SAEs are summarized: by treatment group, by MedDRA preferred term.

- An AE is considered 'Serious' whether or not it is a TEAE.
- An AE is considered in the 'Other' category if it is both a TEAE and is not serious. For each Serious AE and 'Other' AE, for each term and treatment group, the following are provided:
 - the number of participants at risk of an event
 - the number of participants who experienced each event term
 - the number of events experienced.
- For each SAE, these additional terms are provided for EudraCT:
 - the total number of occurrences causally related to treatment

- the total number of deaths
- the total number of deaths causally related to treatment.
- Consistent with www.ClinicalTrials.gov requirements, ‘Other’ AEs that occur in fewer than 5% of patients/subjects in every treatment group may be excluded if a 5% threshold is chosen. Allowable thresholds include 0% (all events), 1%, 2%, 3%, 4%, and 5%.
- AE reporting is consistent with other document disclosures for example, the CSR, manuscripts, and so forth.

7. Unblinding Plan

The purpose of this unblinding plan is to maintain the scientific integrity of the study. The following actions/procedures will be put in place prior to any unblinding of the study data.

This is a double-blind study where investigators and patients are not aware of their assigned treatment. Study treatment codes will be scrambled in the analysis data sets until the primary database lock and therefore, there will be no other unblinding for this study.

8. References

- Baghurst PA. Calculating the mean amplitude of glycemic excursion from continuous glucose monitoring data: an automated algorithm. *Diabetes Technol Ther*. 2011;13(3):296-302.
- Clarke W, Kovatchev B. Statistical tools to analyze continuous glucose monitor data. *Diabetes Technol Ther*
- Hirsch IB. Glycemic variability: It's not just about A1c anymore! *Diabetes Technol Ther*. 2005;7(5):780-783.

9.1. Derivation of CGM Variables

9.2. General Derivation Specifications

All CGM variables will be derived for each patient, for each time interval of each study period (lead-in, Period I and Period II), based upon the data from valid CGM session days (Section 6.12). For Period I and Period II, the variables will be derived for 0-4, 2-6 (interstitial glucose reduction rates only), 0-6, and 4-6 weeks relative to the start of each randomized treatment period, respectively.

If any concentration below lower limit of quantification (LOQ) or above upper LOQ are identified, they will be treated as LOQ for calculation of the CGM parameters. No missing CGM values will be imputed.

Since the CGM values may not be measured at the exact same time for each day for a specific individual patient, due to device changes or gaps in usage, non-overlapping intervals ('buckets') of 5 minutes over 00:00:00 to 23:59:59 (00:00:00 to 00:04:59, 00:05:00 to 00:09:59, etc.) will be used for any derivations requiring time-matched measurements across days within a visit (e.g., mean of daily difference [MODD]).

All CGM parameters will be estimated to precision of 1 decimal place, unless stated otherwise. All CGM glucose derivations will be conducted in units of mg/dL and mmol/L.

Only readings collected from valid CGM days while patients are on pump and on IP, will be included in the derived.

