6. To compare LY900014 and insulin lispro with respect to the interstitial glucose reduction rate from hyperglycemia following a non-meal-related correction bolus delivered via the pump	6. Interstitial glucose reduction rate (glucose reduction [mg/dL and mmol/L] per minute) within 4 hours following a non-meal-related correction bolus via the pump, from hyperglycemia (interstitial glucose >180 mg/dL (10.0 mmol/L) to recovery (interstitial glucose ≤180 mg/dL), from up to 6 weeks of CGM use

Objectives	Endpoints
7. To compare LY900014 and insulin lispro with respect to the rate of severe hypoglycemic events	7. Rate (events/patient/100 years) of severe hypoglycemic events during the 6-week treatment period
Tertiary/Exploratory Objectives	
8. To compare the safety of LY900014 and insulin lispro	8. Adverse events and vital signs
9. To compare LY900014 and insulin lispro with respect to the rate and incidence of documented symptomatic post-meal hypoglycemia	9. Rate (events/patient/year and/or events/patient/30 days) and incidence (percent of patients with at least 1 event) of documented symptomatic post-meal hypoglycemia within 1 and 2 hours after the start of a meal during the last 2 weeks of the 6-week treatment period
10. To compare LY900014 and insulin lispro with respect to the rate and incidence of documented symptomatic hypoglycemia	10. Rate (events/patient/year and/or events/patient/30 days) and incidence (percent of patients with events) of documented symptomatic hypoglycemic events during the last 2 weeks of the 6-week treatment period
11. To compare LY900014 and insulin lispro with respect to the incremental AUCs after breakfast, obtained from CGM use	11. Incremental AUC _{0-1 hour} after breakfast during the last 2 weeks of up to 6 weeks of CGM use
12. To compare LY900014 and insulin lispro with respect to the duration of time glucose values are within target range (71 and 180 mg/dL [3.9 and 10.0 mmol/L]), obtained from CGM use	12. Duration (in minutes) and percentage of time with glucose values between 71 and 180 mg/dL (3.9 and 10.0 mmol/L), both inclusive, normalized to a 24-hour period, during the last 2 weeks of up to 6 weeks of CGM use

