Time interval until infusion set change	All Patients in the Safety Population with a baseline and a post-baseline observation	From first to last dose of open-label insulin lispro, excluding data (if any) that are collected while patients temporarily are off pump or off open-label insulin lispro	From first to last dose of IP in each randomized treatment period (Period I and Period II), excluding data (if any) that are collected while patients temporarily are off pump or off IP
Basal, bolus, and total insulin doses, bolus/total insulin dose ratios	All Patients in the Randomized Population with a baseline and a post-baseline observation	Visit 3 prior to first dose of IP	Visits 4, 6, 7, and 9 prior to last dose of IP in each randomized treatment period (Period I and Period II)
CGM outcome variables (including interstitial glucose reduction rate)	All Patients in the CGM Population (with a baseline and a post-baseline observation for continuous variables, unless otherwise ²)	From first to last dose of open-label insulin lispro, excluding data (if any) that are collected while patients temporarily are off pump or off open-label insulin lispro	From first to last dose of IP in each randomized treatment period (Period I and Period II), excluding data (if any) that are collected while patients temporarily are off pump or off IP
Hypoglycemia events	All Patients in the Safety Population	From first to last dose of open-label insulin lispro	Visits 4, 5, 6, 7, 8 and 9 after first dose of IP and prior to last dose of IP in each randomized treatment period (Period I and Period II)
HbA1c summary statistics	All Randomized Patients with a baseline and at least one post-baseline observation while on IP	Last of Visit 1-3 prior to the first dose of IP	Visits 6 and 9

Study Period/Analysis	Patient Population	Baseline Observations	Post-Baseline Observations
1,5 AG	All Randomized Patients with a baseline and at least one post-baseline observation while on IP	Last of Visit 1-3 prior to the first dose of IP	Visits 6 and 9

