9.3. Interstitial Glucose Reduction Rate following a Correction Bolus via the Pump

The interstitial glucose reduction rate (mg/dl per minute and mg/dl per minute per unit of insulin dose) within 4 hours following a non-meal-related correction dose via the pump will be calculated by dividing the interstitial glucose reduction by the time it takes to first recover (≤ 180 mg/dL) from hyperglycemia after the correction dose. The interstitial glucose reduction rate will also be analyzed by sub-intervals of interstitial glucose levels at the time of the non-meal-related correction bolus: 180 to 250, 250 to 300, and >300 mg/dL (10 to 13.9, 13.9 to 16.7, and >16.7 mmol/L). The interstitial glucose levels at the time of the non-meal-related correction bolus, is defined as the most recent interstitial glucose within 1 hour prior to the correction bolus.

The non-meal related correction boluses delivered by pump will be derived through the following steps:

- Step 1: pull all correction boluses captured in eCOA;
- Step 2: exclude those correction boluses delivered through syringe;

- Step 3: exclude those associated with the last prior SMBG within 1 hour ≤ 180 mg/dl and the last post SMBG within 2 hours increases from prior SMBG. These correction boluses should not have been reported as non-meal related;
- Step 4: remove duplicate correction boluses. If 2 correction boluses are reported for the exact same time, only 1 correction bolus will be included;
- Step 5: if within 4 hours a second correction bolus is given before recovery (≤ 180 mg/dl), only the first non-meal-related correction bolus time will be used and the data after the second correction bolus will be censored. If the glucose never recovered to ≤ 180 mg/dL within 4 hours before any other correction boluses are given, the glucose reduction rate will be calculated by dividing the greatest glucose reduction within 4 hours before any other correction bolus, by the time it took to reach this level.

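### The SAP's 1-decimal default for CGM parameters is too coarse for the interstitial glucose reduction rate in mmol/L per minute and for the per-unit rate (minor)

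*SAP*

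**What the plan says.** SAP 9.2 (General Derivation Specifications) gives two rules side by side. The first is on precision: "All CGM parameters will be estimated to precision of 1 decimal place, unless stated otherwise". The second is on units: "All CGM glucose derivations will be conducted in units of mg/dL and mmol/L".

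The reduction rate falls under both. SAP Table ITSI.6.2 lists it among the CGM variables: "CGM outcome variables (including interstitial glucose reduction rate". Endpoint 6 in SAP Table ITSI.4.1 is defined in both units: "Interstitial glucose reduction rate (glucose reduction [mg/dL and mmol/L] per minute) within 4 hours following a non-meal-related correction bolus via the pump". Table ITSI.6.8 and the protocol's Table ITSI.2 define it the same way.

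SAP 9.3 derives the rate by "dividing the interstitial glucose reduction by the time it takes to first recover" to 180 mg/dL or below. It names the units as "mg/dl per minute and mg/dl per minute per unit of insulin dose", which adds a per-unit version that is not in the endpoint definition. Neither 9.3, nor 6.12, nor Table ITSI.6.8 states a precision for the rate, so the exception in 9.2 for cases stated otherwise is not used and the default applies.

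**The concern.** One decimal suits glucose in mg/dL, minutes in range or percentages. It does not suit a per-minute rate in mmol/L, where plausible values lie near or below the size of one rounding step. Endpoint 6 is the secondary measure of how quickly each insulin brings down hyperglycemia after a correction bolus. If the rule is followed as written, one of its two required units would consist almost entirely of 0.0 and 0.1, and could disagree with the mg/dL version of the same data. The per-unit rate has the same weakness to a lesser degree.

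**Working it through.** **Inputs from the documents**
- Precision: 1 decimal (SAP 9.2).
- Window: 4 hours, or 240 minutes (endpoint 6).
- Recovery level: 180 mg/dL (SAP 9.3).
- Starting-glucose bands and conversion: "180 to 250, 250 to 300, and >300 mg/dL (10 to 13.9, 13.9 to 16.7, and >16.7 mmol/L" (SAP 9.3). 180/10.0 = 18.0 and 250/13.9 = 17.99, so 1 mmol/L is taken as 18 mg/dL.

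The documents give no reduction rates, recovery times or correction-bolus sizes. Where these enter below, they are assumptions.

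**1. The SAP's own example of 1-decimal precision (SAP 9.6).** 135/3078 = 4.386%, shown as 4.4%. 135/3078 × 1440 = 63.158, shown as 63.2 minutes. Both reproduce. Rounding the percentage first would give 0.044 × 1440 = 63.36, or 63.4. So the example rounds the final parameter and not the intermediate step.

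**2. Rounding thresholds in mmol/L/min.**
- Rounds to 0.0: rate below 0.05 mmol/L/min, and 0.05 × 18 = 0.9 mg/dL/min.
- Rounds to 0.1: rate from 0.05 to below 0.15 mmol/L/min, and 0.15 × 18 = 2.7 mg/dL/min.

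**3. What this means in recovery time.** With rate = (start − 180)/minutes, the value is 0.0 when minutes exceed (start − 180)/0.9.

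| Start (mg/dL) | Calculation | Recorded as 0.0 if recovery takes longer than |
|---|---|---|
| 200 | 20/0.9 | 22 min |
| 220 | 40/0.9 | 44 min |
| 250 | 70/0.9 | 78 min |
| 300 | 120/0.9 | 133 min |
| 350 | 170/0.9 | 189 min |

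For example, 250 to 180 mg/dL in 90 minutes is 70/90 = 0.78 mg/dL/min, and 0.78/18 = 0.043 mmol/L/min, which rounds to 0.0.

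**4. Share of zeros and distortion if values are rounded before analysis.** Gamma-distributed rates were simulated; the means and SDs are assumptions.

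| Assumed means (SD), mg/dL/min | Share recorded as 0.0 mmol/L/min | Change in the mmol/L treatment difference |
|---|---|---|
| 0.5 and 0.6 (0.3) | 90% and 85% | −10% |
| 0.7 and 0.85 (0.4) | 74% and 61% | +57% |
| 1.0 and 1.2 (0.4) | 45% and 24% | +91% |
| 1.2 and 1.4 (0.5) | 30% and 15% | +41% |
| 1.5 and 1.8 (0.6) | 15% and 4% | about −11% |

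Neither the size nor the direction of the distortion is fixed by the plan.

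**5. If rounding applies to display only.** Means of 0.70 and 0.85 mg/dL/min are 0.039 and 0.047 mmol/L/min. They print as 0.0 and 0.0, with a difference of 0.0. Means of 1.0 and 1.2 mg/dL/min are 0.056 and 0.067 mmol/L/min. They print as 0.1 and 0.1, and their difference of 0.011 prints as 0.0.

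**6. The mg/dL/min version.** The rounding SD is 0.1/√12 = 0.029 mg/dL/min. The same step on the mmol/L scale corresponds to 0.029 × 18 = 0.52 mg/dL/min. In every scenario of step 4, the mg/dL/min treatment difference moved by about 0.1% or less.

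**7. The per-unit rate.** The maximum error is 0.05 mg/dL/min/U, so the maximum relative error is 0.05/value. At 0.50 it is 10%; at 0.30, 17%; at 0.15, 33% (recorded as 0.2). At 0.05 it is 100% (recorded as 0.1), and any value below 0.05 is recorded as 0.0, also a 100% error. With an assumed 0.3 mg/dL/min, a 2 U bolus gives 0.15 and a 6 U bolus gives 0.05.

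**The case against.** The strongest reply is that the 1-decimal rule is a reporting convention. The SAP does not say that values are rounded before they enter the mixed model, and the example in SAP 9.6 carries the unrounded ratio forward. A programmer would probably notice a table of 0.0 values. The mmol/L rate is also only a linear rescaling of the mg/dL rate, which keeps its resolution. Endpoint 6 is one of several secondary endpoints without multiplicity control, in a study that the plan says is not powered for non-inferiority or superiority.

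Much of this stands. The text does not settle whether rounding precedes analysis, so it cannot be said that the analysed mmol/L means and differences will be wrong. The mg/dL/min comparison survives on either reading. What does not stand is that a display-only reading cures the problem: step 5 shows that the mmol/L table would still be uninformative.

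A reader might also infer that most mmol/L values will be zero, or that the treatment difference will be inflated by a particular amount. The documents do not support either, because they give no rates. Zeros are a majority only if typical rates lie below about 0.9 mg/dL/min. That is likely for starts of 180 to 250 mg/dL with slow recovery, but not in general for starts above 300. Nor is a third a ceiling for the per-unit error: it holds only for values of 0.15 mg/dL/min/U or more.

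**Conclusion.** The point holds, with minor consequence. As written, the default precision covers endpoint 6 and makes one of its two required units too coarse to be informative: every rate below 0.9 mg/dL/min becomes 0.0 mmol/L/min, and every rate from there to below 2.7 becomes 0.1. These thresholds follow from the SAP's rule and the unit conversion alone. The share of zeros, about 4% to 90%, rests on assumed mean rates from 1.8 down to 0.5 mg/dL/min. The per-unit error of up to 0.05 mg/dL/min/U follows from the rule, but its relative size depends on bolus sizes that the documents do not give, and that rate is not part of endpoint 6 as defined. It would be wrong to conclude that endpoint 6 is lost or that its treatment comparison is invalid. The mg/dL/min analysis is essentially unaffected, and the primary endpoint is not touched.

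**What to change.** In SAP 9.2, state that CGM parameters are derived and analysed at full precision and that rounding applies to display only. For the interstitial glucose reduction rate, display at least 2 decimals in mg/dL/min, 3 in mmol/L/min and 3 for the per-unit versions. With 3 decimals in mmol/L/min, the maximum rounding error falls from 0.05 to 0.0005 mmol/L/min, which is 0.0005 × 18 = 0.009 mg/dL/min. The cost is a sentence or two in the SAP and the matching table formats, with no new data and no change of method.

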9.3. Interstitial Glucose Reduction Rate following a Correction Bolus via the Pump

The interstitial glucose reduction rate (mg/dl per minute and mg/dl per minute per unit of insulin dose) within 4 hours following a non-meal-related correction dose via the pump will be calculated by dividing the interstitial glucose reduction by the time it takes to first recover (≤ 180 mg/dL) from hyperglycemia after the correction dose. The interstitial glucose reduction rate will also be analyzed by sub-intervals of interstitial glucose levels at the time of the non-meal-related correction bolus: 180 to 250, 250 to 300, and >300 mg/dL (10 to 13.9, 13.9 to 16.7, and >16.7 mmol/L). The interstitial glucose levels at the time of the non-meal-related correction bolus, is defined as the most recent interstitial glucose within 1 hour prior to the correction bolus.

The non-meal related correction boluses delivered by pump will be derived through the following steps:

- Step 1: pull all correction boluses captured in eCOA;
- Step 2: exclude those correction boluses delivered through syringe;

- Step 3: exclude those associated with the last prior SMBG within 1 hour ≤ 180 mg/dl and the last post SMBG within 2 hours increases from prior SMBG. These correction boluses should not have been reported as non-meal related;
- Step 4: remove duplicate correction boluses. If 2 correction boluses are reported for the exact same time, only 1 correction bolus will be included;
- Step 5: if within 4 hours a second correction bolus is given before recovery (≤ 180 mg/dl), only the first non-meal-related correction bolus time will be used and the data after the second correction bolus will be censored. If the glucose never recovered to ≤ 180 mg/dL within 4 hours before any other correction boluses are given, the glucose reduction rate will be calculated by dividing the greatest glucose reduction within 4 hours before any other correction bolus, by the time it took to reach this level.

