The definition and derivation of these variables are described in detail in 9.1.

Table ITSI.6.8. Outcome Measures of CGM DATA

Category	Endpoints	24-Hour	Daytime ¹	Nighttime ²	Breakfast ³
Interstitial Glucose Reduction Rate following a Correction Bolus via the Pump (mg/dl/min and mg/dl) ⁴					
	Interstitial glucose reduction rate (glucose reduction [mg/dL and mmol/L] per minute) within 4 hours following a non-meal-related correction bolus via the pump, from hyperglycemia (interstitial glucose >180 mg/dL (10.0 mmol/L) to recovery (interstitial glucose \leq 180 mg/dL)	across all non-meal-related correction doses via the pump			
	Interstitial glucose reduction rate (glucose reduction [mg/dL and mmol/L] per minute) within 4 hours following a non-meal-related correction bolus via the pump, from hyperglycemia (interstitial glucose >180 mg/dL [10.0 mmol/L] and \leq 250 mg/dL [13.9 mmol/L]) to recovery (interstitial glucose \leq 180 mg/dL)	across all non-meal-related correction doses via the pump			

Category	Endpoints	24-Hour	Daytime ¹	Nighttime ²	Breakfast ³
	Interstitial glucose reduction rate (glucose reduction [mg/dL and mmol/L] per minute) within 4 hours following a non-meal-related correction bolus via the pump, from hyperglycemia (interstitial glucose >250 mg/dL [13.9 mmol/L] and ≤300 mg/dL [16.7 mmol/L]) to recovery (interstitial glucose ≤180 mg/dL)	across all non-meal-related correction doses via the pump			
	Interstitial glucose reduction rate (glucose reduction [mg/dL and mmol/L] per minute) within 4 hours following a non-meal-related correction bolus via the pump, from hyperglycemia (interstitial glucose >300 mg/dL [16.7 mmol/L] to recovery (interstitial glucose ≤180 mg/dL)	across all non-meal-related correction doses via the pump			
Incremental AUCs (iAUCs) after Meals					
	iAUC _{0-1hr}				x
	iAUC _{0-2hr}				x
Average Glucose Excursions					
	average glucose excursion 0 to 1 hours				x
	average glucose excursion 0 to 2 hours				x
Glucose in the Target Ranges					
	Duration (in minutes) and percentage of time with glucose values within target range 71 to 180 mg/dL [3.9 and 10.0 mmol/L], both inclusive	x	x	x	x ⁵
	Duration (in minutes) and percentage of time with glucose values within target range 71 to 140 mg/dL [3.9 and 7.8 mmol/L], both inclusive	x	x	x	x ⁵
	Duration (in minutes) and percentage of time with glucose values ≤180 mg/dL [10.0 mmol/L]	x	x	x	x ⁵
Hypoglycemic Episodes					

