9.5. Average Glucose Excursions

Average glucose excursions 0 to 1 hours and 0 to 2 hours will be calculated by averaging all excursion values within 1 or 2 hours. Excursions will be derived by subtracting glucose values by the starting glucose concentration, which is the average of the CGM values in the time window [-19, 0] mins relative to the start of the meal (at most 3 ISIG glucose measures).

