9.7. Hypoglycemic/Hyperglycemic Episodes

Hypoglycemic/hyperglycemic episodes as measured by CGM data are defined as at least 10 consecutive minutes below/above the specified threshold, and determined by 3 or more consecutive CGM values meeting the criterion.

The number of distinct hypoglycemic episodes that start will be derived along with days of CGM use (Section 6.12) to calculate the rate of hypoglycemic episodes during a 24-hour period. For example, the rate of postprandial hypoglycemic episodes (≤ 70 mg/dL [3.9 mmol/L]), during the 24-hour period, will be calculated with the following steps:

- Step 1: identify all events as runs of 3 or more consecutive CGM values meeting the criterion, where the pre-marker glucose value (≤ 70 mg/dL [3.9 mmol/L]). Consecutive implies no gaps in time more than 6 minutes between measurements. Events will be identified without regard for the CGM level prior to the start of the Carb event.
- Step 2: Count the number of distinct events over the 24-hour period.
- Step 3: Calculate rate per month by multiplying count by 30/days of CGM use. Days of CGM use will be calculated as the number of observations during the 24-hour period divided by the observation supposed to be measured during the period (288 observations for the 24-hour period).

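### Secondary endpoint 6: the glucose reduction rate depends strongly on the starting glucose, and the all-bolus model does not adjust for it

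*SAP*

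**What the plan says.** Endpoint 6 (SAP Table ITSI.4.1) runs "from hyperglycemia (interstitial glucose >180 mg/dL (10.0 mmol/L) to recovery (interstitial glucose ≤180 mg/dL", so entry and exit share one cut-off. SAP 9.3 obtains the rate by "dividing the interstitial glucose reduction by the time it takes to first recover", in the period "within 4 hours following a non-meal-related correction dose via the pump". The starting value "is defined as the most recent interstitial glucose within 1 hour prior to the correction bolus": one reading, not an average. If 180 is never reached, the rate comes from "dividing the greatest glucose reduction within 4 hours before any other correction bolus" and the time taken to reach that level. No minimum fall and no confirming reading are stated.

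Results are also planned by starting level (180-250, 250-300 and above 300 mg/dL). The model in SAP 6.12 and Protocol 10.3.3.2 has treatment, period and sequence as fixed effects and patient as random. It has no term for starting glucose. I read it as fitted to individual boluses.

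For hypo- and hyperglycemic episodes the same SAP asks for confirmation: they are "determined by 3 or more consecutive CGM values meeting the criterion" (SAP 9.7).

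**The concern.** A correction bolus takes time to act. If glucose starts just above 180, most of the time to recovery is that initial lag, and the fall being divided is small. If it starts at 300, the lag is a minor part. The same insulin in the same patient therefore yields very different rates according to where the bolus was given.

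Two things follow. Spread in starting glucose inflates the variability of the rate, which costs precision. And if patients correct at somewhat different glucose levels on the two insulins, the comparison shifts for reasons unrelated to speed of action. The single-reading end point adds a lesser problem: near 180, one low reading can end the measurement before any real fall.

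**Working it through.** The plan states no effect size, variability or sensor error for this endpoint, so it has no figure of its own to reproduce. The one reproducible design figure, 42/(1 - 0.12) = 47.7, rounded up to 48 randomized (SAP 5.2), does not bear on it.

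**Inputs from the documents:** start above 180, recovery at or below 180, 4-hour window, bands and model (SAP 6.12 and 9.3); readings every 5 minutes (Protocol 5.1). **Assumed:** a fall of 1 mg/dL/min after a lag L of 20 min (faster insulin) or 30 min (slower insulin), and the sensor error.

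**Step 1. Rate by starting level.** With D = start - 180, time to recovery is L + D, so rate = D/(L + D).

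| Start | L = 20 | L = 30 | Difference |
|---|---|---|---|
| 185 | 5/25 = 0.20 | 5/35 = 0.14 | 0.06 |
| 200 | 20/40 = 0.50 | 20/50 = 0.40 | 0.10 |
| 250 | 70/90 = 0.78 | 70/100 = 0.70 | 0.08 |
| 300 | 120/140 = 0.86 | 120/150 = 0.80 | 0.06 |

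For one insulin (L = 20), the rate moves by 0.58 between 185 and 250, but by only 0.08 between 250 and 300. The 180-250 band thus keeps most of the dependence, and the 250-300 band has little.

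**Step 2. Precision without any noise.** Take D uniform on 0 to 120. The mean rate is 1 - (L/120) × ln((L + 120)/L).
- L = 20: 1 - 0.1667 × 1.946 = 0.676.
- L = 30: 1 - 0.25 × 1.609 = 0.598.
- Difference: 0.078.

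The mean square is 1 - 2(1 - mean) + L/(L + 120).
- L = 20: 1 - 0.649 + 0.143 = 0.494, so SD = √(0.494 - 0.457) ≈ 0.19.
- L = 30: 1 - 0.805 + 0.200 = 0.395, so SD = √(0.395 - 0.357) ≈ 0.19.

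The per-bolus standardized difference is about 0.078/0.195 = 0.40. All of that spread is starting level.

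**Step 3. Adding sensor noise.** I simulated the same contrast on 5-minute readings with autocorrelated error, for starts of 180-300. The standardized difference was 0.44-0.45 with no noise, 0.45-0.46 with SD 5 mg/dL and autocorrelation 0.8, 0.41 with SD 5 and 0.5, and 0.39 with SD 8 and 0.8. The absolute difference stayed at about 0.08 in the no-noise and SD 5 (0.8) runs. By band (SD 5, 0.8), the standardized difference was 0.49 for 180-250 and 1.25 for 250-300. A second simulation with variable slopes, and starts concentrated near 180, gave an absolute difference of 0.097 without noise and 0.094-0.101 with it. There the standardized difference fell from 0.40 to 0.34 (SD 10, autocorrelation 0.9) or 0.15 (SD 10, 0.5), so noise matters when it is large or weakly correlated.

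**Step 4. A shift in where patients correct.** With L = 20 and no noise, moving starts from 180-240 to 190-250 changes the mean rate from 1 - (20/60) ln(80/20) = 0.54 to 1 - (20/60) ln(90/30) = 0.63, a change of 0.10. In simulation with noise it went from 0.62 to 0.67. Against a treatment effect of 0.08, a shift of about 8 mg/dL (10 × 0.08/0.10) to 16 mg/dL (10 × 0.08/0.05) in starts in this range would equal or cancel it.

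**Step 5. False recoveries on flat glucose.** With error SD 5 to 15 and autocorrelation 0.5 or 0.9, the chance of a single reading at or below 180 within 4 hours was 78-100% at a true level of 185, 27-100% at 190, 0.1-96% at 200, 0-15% at 220 and about 0% from 250. At SD 5, for starts reading 181-200, the median rate of these false recoveries was 0.18-0.28 and the 90th percentile 0.7-1.2. Most are slow. A case such as 184 to 179 in 5 minutes (1.0 mg/dL/min) is in the tail.

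**Step 6. What the remedies buy.** A starting-glucose covariate raised the standardized difference from 0.46 to 0.73 with a uniform slope, and from 0.30 to 0.34 with variable slopes. Three-reading confirmation did not reduce it: 0.34 to 0.36 at SD 10 and autocorrelation 0.9, 0.15 to 0.27 at SD 10 and 0.5.

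**The case against.** A reader might infer more: that sensor noise alone produces many fast recoveries and so shrinks the insulin comparison. The documents do not support that. They give no sensor error and no distribution of starting glucose. Under assumed values the absolute difference hardly moves, and most of the loss is present with no noise at all. False recoveries are frequent only near 180. Over all starts above 180 in the flat-glucose simulation they were 4-13% (assumed SD 3-8), and flat glucose after a bolus is not the trial setting.

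The plan also has partial safeguards. The bands condition on starting level, and those above 250 are largely sound. SAP 9.3 adds a rate per unit of insulin, drops some boluses whose prior SMBG was at or below 180 and then rose, and censors at a second bolus. Blinding and the crossover make a systematic difference in correction level less likely, and none is shown. All of this stands, but the all-bolus comparison and the lowest band remain exposed.

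The most serious objection is to the remedy. Starting glucose is measured after randomization and may itself respond to treatment, so adjusting for it could remove part of a real effect. That also stands, and is why the unadjusted result must be shown beside the adjusted one.

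**Conclusion.** The point holds as one of precision and comparability. The rate mixes insulin action with starting glucose, and the planned all-bolus model leaves that mixture in. In the worked example the same response scores 0.20 from 185 and 0.86 from 300. It does not follow that the estimated treatment difference is materially biased toward zero. The single-reading end point is a secondary matter for starts within about 20 mg/dL of 180, and its importance cannot be sized from the documents.

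The dependence on starting level follows from the definition whenever there is a lag. The amounts rest on the assumed lag, slope and noise, and the gain from adjustment ranges from small to substantial with them. Endpoint 6 is secondary, without multiplicity control, in a trial not powered for superiority or non-inferiority. The change could usefully be made; the primary endpoint uses SMBG and pump alarms and is not affected.

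**What to change.** In SAP 6.12, add glucose at the time of the bolus, as already defined in SAP 9.3, as a covariate in the model for the reduction rate. In SAP 9.3, date recovery at the first of three consecutive readings at or below 180 mg/dL, following SAP 9.7. Keep the current single-reading, unadjusted derivation as a supportive analysis and report it next to the adjusted one, noting that the covariate is post-randomization.

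Averaging the start, as SAP 9.5 does for excursions, and restricting to starts of 200 mg/dL or more are optional and not needed. While editing, reconcile the recovery cut-off: Protocol 10.3.3.2 uses below 180, whereas the endpoint and SAP 9.3 use at or below 180.

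The cost is SAP wording and programming on CGM data already collected, to be settled before unblinding, plus one extra result to present.
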